• Table 1.2 Schedule of Events: Treatment-Free Period of Treatment-Free/Re-Treatment Cohort	
 • Add clarifying language for ECG timing (moved from vitals assessments) and frequency (also in Section 8.4.5 Other Safety) 	
• Table 1.3 Schedule of Events: Re-Treatment Period of Treatment-Free/Re-Treatment Cohort	
 • Separate out TSH from hormone testing (also in Section 8.4.3 Clinical Laboratory Evaluations and Table 10.1 Clinical Laboratory Tests) • Update visits when dosing diary is provided to patients • Add a row for collection of End of Study form • Defined a month as a 28-day interval for the M1/M2 visit for retreatment patients in the Treatment-Free/Re-Treatment 	

CONVENTIONS USED IN THIS SUMMARY OF CHANGES

	
Cohort and as a 30-day interval for all other cohorts/visits
 
(Table 1.1 and 1.3 only)
 
 Clarified that MRI scans are required every 6 months for subjects in the Treatment Continuation Cohort and every 3 months for those in the Treatment-free period and Re-Treatment periods of the Treatment-Free/Re-Treatment Cohort (also in Sections 1 Protocol Summary and 4.1.1 Design Overview) Clarified that subjects from Treatment Free/Re-Treatment Cohort restarting treatment should note MRI as due to progression and use the BL2 assessment as reference (also in Section 4.1.1 Design Overview) Clarified that urinalysis assessments will be performed at 6-month intervals (also in Section 1 Protocol Summary) Separated EOT and EOS/AE Follow-up as 2 separate visits and reinforced that EOT must occur within 24 months after enrollment Removed entry for on-site study drug administration (also in Section 6.2.2 Administration) 
(Table 1.2 only)
 
 Updated visits to: 
 make M12 its own visit combine M24 and EOT make EOS/AE Follow-up its own visit Removed comments language for AE and ConMed rows 	

 4.1.1 Design Overview Table 10.1 Clinical Laboratory Tests 	
Added coagulation, ECG, and hormone testing to list of ongoing safety monitoring and made albumin globulin (A/G) ratio optional
	
Completeness of list

 4.1.3 Dose Regimen 6.1 Study Drug(s) Description 	
Reinforced message that dose escalations are not permitted
	
Reinforcing existing language

1. PROTOCOL SUMMARY

1.1. Protocol Synopsis

Protocol Title
A Phase 4, Multicenter Study to Evaluate Discontinuation and Re-Treatment in Subjects with Tenosynovial Giant Cell Tumor (TGCT) Previously Treated with Pexidartinib
Protocol Short Title
Pexidartinib TGCT Continuation Study
Protocol Number
PL3397-A-U4003
Sponsor/Collaborators
Daiichi Sankyo Inc Daiichi Sankyo Europe GmbH, a Daiichi Sankyo Company
Registry Identification(s)

• NCT Number: NCT04526704• EudraCT Number: 2020-000192-20
IND Number
117,332
Study Phase
Phase 4
Planned Geographical Coverage, Study Sites, and Location
US, EU (Netherlands, Spain, Hungary, and Italy), Australia, and Taiwan
Study Population
Subjects with TGCT (pigmented villonodular synovitis [PVNS] or giant cell tumor of the tendon sheath [GCT-TS]) who are currently being treated with pexidartinib in one of the following studies (hereafter referred to as prior study): PLX108-10 (ENLIVEN), PLX108-01, PL3397-A-A103, or PL3397-A-U126.

Study Objectives/Outcome Measures and Endpoints

The Table below lists primary and secondary study objectives and endpoints which have outcome measures.

I. Treatment-Free/Re-Treatment Cohort

Period	Objectives	Outcome Measure	Endpoints	Category
Primary Objective				
Overall	Proportion of subjects who remain treatment-free	
Title: Proportion of treatment-free subjects at 12 months and 24 months
 
Description: Proportion of subjects who remain treatment-free at Month 12 and Month 24
 
Time frame: 24 months after last subject enrolled in the Cohort
	Proportion of subjects who remain treatment-free at Month 12 and Month 24	Efficacy
Secondary Objectives				
Treatment-Free period	Change from Baseline in Patient Reported Outcomes (PROs)	
Title: Change from Baseline in PROs
 
Description: Change from Baseline in PROs (PROMIS PF, EQ-5D-5L)
 
Time frame: 24 months after last subject enrolled in the Cohort
	Mean change from Baseline* for PROMIS PF and EQ-5D-5L quarterly for the treatment-free and Re-Treatment periods. *Note: Baseline is Screening values.	Efficacy
	Safety	
Title: Number of subjects with AE during the Treatment-Free period*
 
Description: Total number of subjects in the safety analysis set with any AE collected between Screening and start of re-treatment or final database lock (whichever occurs first)
 
Time frame: 24 months after last subject enrolled in the Cohort
 
*Note: Listed as a secondary objective but is a primary outcome measure.
	Incidence of AEs and SAEs, ECGs, and laboratory assessments	Safety
Re-Treatment period	Tumor Assessment	
Title: Tumor assessment
 
Description: Investigator evaluation of tumor
 
Time frame: 24 months after last subject enrolled in the Cohort
	Qualitative assessment of the tumor	Efficacy
	Change from Baseline in Patient Reported Outcomes (PROs)	
Title: Change from Baseline in PROs
 
Description: Change from Baseline in PROs (PROMIS PF, EQ-5D-5L)
 
Time frame: 24 months after last subject enrolled in the Cohort
	Mean change from Baseline* for PROMIS PF and EQ-5D-5L quarterly for the retreatment periods. *Note: Baseline is reinitiated with subject entering Re-Treatment period.	Efficacy
	Safety	
Title: Number of subjects with AE during the Re-Treatment period*
 
Description: Total number of subjects in the safety analysis set with any AE collected between first re-treatment dose and final database lock
 
Time frame: 24 months after last subject enrolled in the Cohort
 
*Note: Listed as a secondary objective but is a primary outcome measure.
	Incidence of TEAEs and SAEs, ECGs, and laboratory assessments	Safety

II. Treatment Continuation Cohort

Objectives	Outcome Measure	Endpoints	Category
Primary Objective			
None			
Secondary Objectives			
Tumor Assessment	
Title: Tumor assessment
 
Description: Investigator evaluation of tumor
 
Time frame: 24 months after last subject enrolled in the Cohort
	Qualitative assessment of the tumor	Efficacy
Change from Baseline in PROs	
Title: Change from Baseline in PROs
 
Description: Change from Baseline in PROs (PROMIS PF, EQ-5D-5L)
 
Time frame: 24 months after last subject enrolled in the Cohort
	Mean change from Baseline* for PROMIS PF and EQ-5D-5L at quarterly assessments. *Note: Baseline is Screening values.	Efficacy
Safety	
Title: Number of subjects with TEAE during the study*
 
Description: Total number of subjects in the safety analysis set with any AE collected between first dose and final database lock
 
Time frame: 24 months after last subject enrolled in the Cohort
 
*Note: Listed as a secondary objective but is a primary outcome measure.
	Incidence of TEAEs and SAEs, ECGs, and laboratory assessments	Safety

AE = adverse event; ECG = electrocardiogram; EQ-5D-5L = EuroQol-Five Dimension Five Level Scale; PRO = Patient-Reported Outcome ; PROMIS PF = Patient-Reported Outcomes Measurement Information System – Physical Function; SAE = serious adverse event; TEAE = treatment emergent adverse event

Study Design

This is a Phase 4, multicenter study in subjects with TGCT (PVNS or GCT-TS) who were previously treated with pexidartinib in one of the following studies: PLX108-10 (ENLIVEN), PLX108-01, PL3397-A-A103, and PL3397-A U126. At the Screening visit/time of consent, at the Investigator and subject's discretion, the subjects are given the choice to either continue treatment with pexidartinib or discontinue treatment with the possibility to reinitiate pexidartinib treatment.

1. Subjects who choose to continue treatment with pexidartinib will be enrolled in the **Treatment Continuation Cohort**. The assessments from the subject's "End-of-Treatment visit" (i.e., the visit on which they received their last dose of study treatment) from their prior study (eg, tumor assessments, PRO measures, and safety parameters) will serve as the Baseline measurements for PL3397-A-U4003 study. These subjects will remain on their current dosage of pexidartinib and undergo clinical assessments at 3-month intervals for the duration of the study.
2. Subjects who choose to discontinue pexidartinib treatment will be enrolled into the Treatment-Free period of the **Treatment-Free/Re-Treatment Cohort**. The assessments from the subject's End-of-Treatment visit from their prior study (eg, tumor assessments, PRO measures, and safety parameters) will serve as the Baseline measurements for PL3397-A-U4003 study. Subjects will discontinue pexidartinib treatment and undergo clinical assessments at 3-month intervals during the Treatment-Free period. Re-treatment with pexidartinib will be based on the discretion of the subject and Investigator. Tumor assessment, subjective and/or functional measures, and safety will be considered in the decision-making process. The rationale for discontinuing and restarting pexidartinib re-treatment will be recorded accordingly.

Subjects in the **Treatment-Free/Re-Treatment Cohort** who enter the Re-Treatment period will be administered pexidartinib at the dose at which they completed the prior study. Dosing is required on an empty stomach (at least

1 hour before or 2 hours after a meal or snack), at approximately the same times of the day, and approximately 12 hours apart. During the Re-Treatment period, Investigators will ensure weekly liver monitoring tests for the first 8 weeks (2 months), then every 2 weeks for 1 month, then once every 3 months or more frequently as directed by the Investigator.

The Investigator will evaluate the MRI scans every 6 months for subjects in the Treatment Continuation Cohort and every 3 months for subjects in the Treatment-Free/Re-Treatment Cohort to perform a qualitative tumor assessment (i.e., stable disease) for subjects in the Treatment Continuation Cohort. Additional imaging assessments may be performed with changes in tumor response(s) as deemed necessary by the Investigator.

Patient Reported Outcomes (PROs) measures will be performed at 3-month intervals for all subjects.

Ongoing safety assessment, laboratory assessments (serum chemistry and hematology), and physical examination will be performed at 3-month intervals and monitored for adverse events (AEs). Note that laboratory assessments for urinalysis will be performed at 6-month intervals.

See [Figure 1.1](#) for the study flow diagram.

Study Duration

The study start is the date when the first subject has signed the informed consent. Subjects will be evaluated for eligibility at the last visit of their prior study.

1. Subjects in the **Treatment Continuation Cohort** will remain on their current dosage of pexidartinib and undergo study assessments at 3-month intervals for a maximum of 24 months.
2. Subjects from the **Treatment-Free/Re-Treatment Cohort** who enter the Treatment-Free period will undergo study assessments 1 month after enrollment, 3 months after enrollment, and then at 3-month intervals for 24 months or until re-treatment with pexidartinib.

Subjects from the **Treatment-Free/Re-Treatment Cohort** who enter the Re-Treatment period will undergo efficacy and safety study assessments at 3-month intervals until the total time within this Cohort reaches 24 months; a new Baseline will be established upon entry into re-treatment. Liver safety assessments will follow a separate schedule.

All subjects will remain on study for a maximum of 24 months. The study will end with the completion of the last subject's 30-day safety follow-up or with their withdrawal from the study. A post-trial access plan, delineating options for access to pexidartinib, will be available for subjects after completing their study participation if the subject is benefiting from the study drug.

Key Eligibility Criteria

Subjects must meet the following key inclusion/exclusion criteria:

Inclusion Criteria:

1. Currently enrolled and have not discontinued pexidartinib treatment in one of the following studies: Study PLX108-10 (ENLIVEN), Study PLX108-01, Study PL3397-A-A103, or Study PL3397-A-U126.
2. Willing and able to complete the PROMIS Physical Function Scale and EQ-5D-5L throughout the study.
3. Willing and able to provide written informed consent prior to any study-related procedures and to comply with all study requirements.
4. Females of reproductive potential must have a negative urine pregnancy test at Screening/Baseline (to be confirmed by a serum pregnancy test taken on the last-treatment visit of their prior study) and should be advised to use an effective,

non-hormonal method of contraception during treatment with pexidartinib and for 1 month after the last dose. Males with female partners of reproductive potential should be advised to use an effective method of contraception during treatment with pexidartinib and for 1 month after the last dose. Female partners of male patients should concurrently use effective contraceptive methods (hormonal or non-hormonal).

Note: A female is considered of reproductive potential following menarche and until becoming postmenopausal (no menstrual period for a minimum of 12 months) unless permanently sterile (undergone a hysterectomy, bilateral salpingectomy or bilateral oophorectomy) with a confirmed by follicle stimulating hormone (FSH) test level >40 mIU/mL.

5. Male subjects must not freeze or donate sperm starting at Screening and throughout the study period, and for at least 5 half-lives or 1 month after the final study drug administration, whichever is longer.

Female subjects must not donate, or retrieve for their own use, ova from the time of Screening and throughout the study treatment period, and for at least 1 month or 5 half-lives after the final study drug administration, whichever is longer.

Exclusion Criteria:

1. Subject has a clinically significant abnormality identified by the Investigator at Screening on physical examination, laboratory tests, or electrocardiogram (ECG) which, in the judgement of the Investigator, would preclude the subject's safe completion of the study.
2. Exposure to another investigational drug or current participation in other therapeutic investigational procedures, besides pexidartinib studies, within 1 month prior to start of study treatment. Any known contraindication to treatment with, including hypersensitivity to, the study drug(s) or excipients in pexidartinib.

Investigational Medicinal Product, Dose, and Mode of Administration

Pexidartinib hydrochloride (HCl) drug substance is an off-white to white solid. Pexidartinib capsules are provided as 200 mg (200 mg free-base equivalent) hypromellose capsules for oral administration containing the following excipients: poloxamer 407, mannitol, crospovidone, and magnesium stearate.

Pexidartinib capsules will be orally administered daily at the subject's current dose of pexidartinib in Study PLX108-10 (ENLIVEN), Study PLX108-01, Study PL3397-A-A103, or Study PL3397-A-U126. Pexidartinib should be administered on an empty stomach (at least 1 hour before or 2 hours after a meal or snack), at approximately the same times of the day, and approximately 12 hours apart.

Active Ingredient(s)/INN

[figure not shown]
Pexidartinib (PLX3397)

Planned Sample Size

Subjects currently enrolled in Studies PLX108-10 (ENLIVEN), PLX108-01, PL3397-A-A103, and PL3397-A-U126 who are eligible for participation in this study.

1.2. Study Schema

Figure 1.1: Study Level Flow Diagram

* Subjects re-initiated on pexidartinib will undergo weekly liver monitoring tests for the first 8 weeks, then every 2 weeks for 1 month, then every 3 months or more frequently as directed by the Investigator.

Note: Screening and Baseline visits will occur on the same day.

1.3. Schedule of Events

Table 1.1: Schedule of Events: Treatment Continuation Cohort

	Visits	SCR	BL	M3	M6	M9	M12	M15	M18	M21	EOT ^a	EOS/AE F/U ^b	Comment
	Window (Days)	0*	0*	±7	±7	±7	±14	±14	±14	±14	±7	±7	* SCR and BL will both occur on EOT visit of preceding study.
Assessments	Procedure												
Informed consent		X											Obtain prior to performing any study procedures
Eligibility assessment			X ^c										
Demographics/Medical history/Prior medications, non-drug therapies, and radiotherapy/Height	N/A												This information will be transferred from prior studies
Vitals	Vital signs and weight	X	X ^c	X	X	X	X	X	X	X	X		
PRO instruments	EQ-5D-5L		X ^c	X	X	X	X	X	X	X	X		Performed before any physical tests
	PROMIS PF		X ^c	X	X	X	X	X	X	X	X		Physical Function Scale performed before any physical tests
Safety	Physical exam	X	X ^c	X	X	X	X	X	X	X	X		Full PE on Screening and EOS, abbreviated PE at other visits. All PE exams will include functional assessment for the affected joint.
	ECG	X	X ^c								X		May be performed whenever deemed medically necessary and at any visit during which a subject exhibits a heart rate ≤50 bpm. Any abnormal finding should be confirmed with a repeated ECG. ECGs should be performed after vital signs assessments.

	Visits	SCR	BL	M3	M6	M9	M12	M15	M18	M21	EOT ^a	EOS/AE F/U ^b	Comment
	Window (Days)	0*	0*	±7	±7	±7	±14	±14	±14	±14	±7	±7	* SCR and BL will both occur on EOT visit of preceding study.
Assessments	Procedure												
AE	TEAE/SAE		X ^c					X			X		See Section 8.4.1
Concomitant medications, non-drug therapies, and radiotherapy	Concomitant		X ^c					X					
Laboratory assessments	Hematology		X ^c	X	X	X	X	X	X	X			See Section 10.2 for details
	Chemistry		X ^c	X	X	X	X	X	X	X			See Section 10.2 for details
	Urinalysis		X ^c		X		X		X		X		See Section 10.2 for details
	Coagulation		X ^c	X	X	X	X	X	X	X	X		See Section 10.2 for details
	Serum pregnancy test	X	X ^d								X		For females of reproductive potential (as defined in Section 5.1)
	Liver function tests		X	X	X	X	X	X	X	X	X		AST, ALT, ALP, total bilirubin, GGT, direct bilirubin
	Hormone testing		X ^c										Females only, FSH to confirm postmenopausal status
	TSH	X	X										
Treatment response/Disease assessment	MRI of affected joint		X ^c		X		X		X		X ^e		Tumor assessment. Additional imaging assessments may be performed with changes in tumor response(s), as deemed necessary by the Investigator.
Dosing Diary	Provide Diary		X	X	X	X	X	X	X	X			Diary for pill count and AEs between scheduled clinic visits
	Review Diary			X	X	X	X	X	X	X	X		

	Visits	SCR	BL	M3	M6	M9	M12	M15	M18	M21	EOT ^a	EOS/AE F/U ^b	Comment
	Window (Days)	0*	0*	±7	±7	±7	±14	±14	±14	±14	±7	±7	* SCR and BL will both occur on EOT visit of preceding study.
Assessments	Procedure												
Study Drug: Pexidartinib	Dispense 3-month supply		X	X	X	X	X	X	X	X			
	Collect returned/Assess treatment compliance		X	X	X	X	X	X	X	X	X		
EOS Form												X	

AE = adverse event; BL = baseline; D = day; ECG = electrocardiogram; EOS = End of Study; EOT = End of Treatment; EQ-5D-5L = European Quality of Life Five Dimension Five Level Scale; FSH = follicle stimulating hormone; FU = Follow-up; M = month; MRI = magnetic resonance imaging; PRO = Patient-Reported Outcome; PROMIS PF = Patient-Reported Outcomes Measurement Information System – Physical Function; SAE = serious adverse events; SCR = screening; TEAE = treatment emergent adverse events; TVS = tumor volume score.

Note: For all visits, a month is considered a 30-day interval.

^a The EOT visit should occur within 7 days after the last dose of pexidartinib or at the time the decision is made to discontinue pexidartinib (if this is more than 7 days after the last dose of pexidartinib), unless there is a medical condition that prevents subjects from completing the visit within this time. The EOT visit must occur within 24 months after enrollment.

^b The End-of-Study will be reached with a follow-up phone call 1-month post-EOT visit to collect AE information.

^c Assessment does not need to be repeated if the procedure was done at End-of-Treatment visit of preceding study.

^d Urine pregnancy test at Screening only.

^e Only subjects who end their study participation early with no radiologic disease progression will have an additional MRI at 3 months ± 14 days after their last dose of study treatment or before any new TGCT therapy, including surgery, whichever occurs first. EOS will occur after this additional MRI.

Table 1.2: Schedule of Events: Treatment-Free Period of Treatment-Free/Re-Treatment Cohort

	Visits	SCR	BL	M1	M3/ M15	M6/ M18	M9/ M21	M12 ^a	M24	EOS/ AE F/U ^b	Comment
	Window (Days)	0*	0*	+ 28	±14	±14	±14	±14	±14	±7	** SCR and BL will both occur on EOT visit of preceding study.
Assessments	Procedure										
Informed consent		X									Obtain prior to performing any study procedures
Eligibility assessment			X								
Demographics/Medical history/Prior medications, non-drug therapies, and radiotherapy/Height	N/A										This information will be transferred from prior studies
Vitals	Vital signs and weight		X ^c	X	X	X	X	X	X		
PRO instruments	EQ-5D-5L		X ^c	X	X	X	X	X	X		Performed before any physical tests
	PROMIS PF		X ^c	X	X	X	X	X	X		Physical Function Scale performed before any physical tests
Safety	Physical exam		X ^c	X	X	X	X	X	X		Full PE at Screening and EOS, abbreviated PE at other visits. All PEs will include functional assessment for the affected joint.
	ECG		X ^c						X		May be performed whenever deemed medically necessary and at any visit during which a subject exhibits a heart rate ≤ 50 bpm. Any abnormal finding should be confirmed with a repeated ECG. ECGs should be performed after vital signs assessments.
AE	AE/SAE		X ^c			X			X		
Concomitant medications, non-drug therapies, and radiotherapy	Concomitant		X ^c			X					

	Visits	SCR	BL	M1	M3/ M15	M6/ M18	M9/ M21	M12 ^a	M24	EOS/ AE F/U ^b	Comment
	Window (Days)	0*	0*	+ 28	±14	±14	±14	±14	±14	±7	** SCR and BL will both occur on EOT visit of preceding study.
Assessments	Procedure										
Laboratory assessments	Hematology		X ^c			X		X	X		See Section 10.2 for details
	Chemistry		X ^c			X		X	X		See Section 10.2 for details
	Urinalysis		X ^c			X		X	X		See Section 10.2 for details
	Coagulation		X ^c			X		X	X		See Section 10.2 for details
	Liver function tests		X			X		X	X		AST, ALT, ALP, total bilirubin, GGT, direct bilirubin
	Urine pregnancy test	X									
	Hormone testing	X ^c	X ^c								Females only, FSH to confirm postmenopausal status
	TSH	X									
Disease assessment	MRI of affected joint		X ^c	X	X	X	X	X	X		Tumor assessment
Dosing Diary	Provide Diary		X	X	X	X	X	X			Diary for AEs between scheduled clinic visits
	Review Diary			X	X	X	X	X	X		
EOS Form										X	

AE = adverse event; BL = baseline; D = day; ECG = electrocardiogram; EOS = End of Study; EOT = End of Treatment; EQ 5D 5L = European Quality of Life Five Dimension Five Level Scale; FSH = follicle stimulating hormone; FU = Follow-up; M = month; MRI = magnetic resonance imaging; PRO = Patient-Reported Outcome; PROMIS PF = Patient-Reported Outcomes Measurement Information System – Physical Function; SAE = serious adverse events; SCR = screening; TVS = tumor volume score.

Note: For all visits, a month is considered a 30-day interval.

Note: In case of early discontinuation from the study, subjects must complete all the assessments corresponding to the M24 visit.

^a Subjects are allowed to continue past 12 months within the Treatment-Free period and will follow quarterly visits as per the 12-month visit until they enter the Re-Treatment period or the EOS, whereupon they will complete the EOS Visit and 30-day safety follow-up.

^b The End-of-Study will be reached with a follow-up phone call 1-month post-last study visit to collect AE information.

^c Assessment does not need to be repeated if the procedure was done at End-of-Treatment visit of preceding study.

Table 1.3: Schedule of Events: Re-Treatment Period^a of Treatment-Free/Re-Treatment Cohort

	Visits	BL-2	M1, M2 (LFT) ^a	M3	M6	M9	Mx ^b	EOT ^c	EOS/ AE FU ^d	Comment
	Window (Days)	0	±3	±3	±14	±14	±14	±7		
Assessments	Procedure									
Vitals	Vital signs and weight	X	X	X	X	X	X			
PRO instruments	EQ-5D-5L	X		X	X	X	X			Performed before any physical tests
	PROMIS PF	X		X	X	X	X			Physical Function Scale performed before any physical tests
Safety	Physical exam	X	X	X	X	X	X			Full PE on EOS, abbreviated PE at first re-treatment and at other visits. All PEs will include functional assessment for the affected joint
	ECG	X						X		May be performed whenever deemed medically necessary and at any visit during which a subject exhibits a heart rate ≤50 bpm. Any abnormal finding should be confirmed with a repeated ECG. ECGs should be performed after vital signs assessments.
AE	TEAE/SAE							X		
Concomitant medications, non-drug therapies, and radiotherapy	Concomitant					X				
Laboratory assessments	Hematology	X	X	X	X	X	X			See Section 10.2 for details
	Chemistry	X	X	X	X	X	X			See Section 10.2 for details
	Urinalysis	X	X		X		X	X		See Section 10.2 for details. Only perform every 6 months (ie, M12, M18, and M24)
	Coagulation	X	X	X	X	X	X			See Section 10.2 for details
	Serum pregnancy test	X	X	X	X	X	X	X		For females of reproductive potential (as defined in Section 5.1)
	Liver function tests ^a	X	X ^a	X	X	X	X	X		

	Visits	BL-2	M1, M2 (LFT) ^a	M3	M6	M9	Mx ^b	EOT ^c	EOS/AE FU ^d	Comment
	Window (Days)	0	±3	±3	±14	±14	±14	±7		
Assessments	Procedure									
	Hormone testing	X								Females only, FSH to confirm postmenopausal status
	TSH	X								
Treatment Response/ Disease Assessment	MRI of affected joint	X ^e		X	X	X	X	X ^f		Tumor assessment. Additional imaging assessments may be performed with changes in tumor response(s) as deemed necessary by the Investigator.
Dosing Diary	Provide Diary		X	X	X	X	X			Diary for pill count and AEs between scheduled clinic visits
	Review Diary			X	X	X	X	X		
	Dispense 3-month supply	X		X	X	X	X			A drug supply for more than 3 months may be dispensed.
Study Drug: Pexidartinib	Collect Returned/ Assess Treatment Compliance			X	X	X	X	X		
EOS Form									X	

AE = adverse event; BL = baseline; D = day; ECG = electrocardiogram; EOS = End of Study; EOT = End-of-Treatment; EQ-5D-5L = European Quality of Life Five Dimension Five Level Scale; FSH = follicle stimulating hormone; FU = Follow-up; M = month; MRI = magnetic resonance imaging; PRO = Patient-Reported Outcome; PROMIS PF = Patient-Reported Outcomes Measurement Information System – Physical Function; SAE = serious adverse events; SCR = screening; TEAE = treatment emergent adverse events; TVS = tumor volume score.

Note: For all visits, a month is considered a 30-day interval, except for the M1/M2 visit for re-treatment patients where there is a 28-day window.

^a Pexidartinib will be administered at the dose at which subject completed the prior study. Doses will be taken on an empty stomach (at least 1 hour before or 2 hours after a meal or snack), at approximately the same times of the day, and approximately 12 hours apart. Weekly liver monitoring tests for the first 8 weeks, then every 2 weeks for 1 month, then every 3 months or more frequently as directed by the Investigator.

^b Patient visits should be done every 3 Months until 21 Months after baseline. The combined overall study duration of all treatment, treatment-free, and re-treatment phases should not exceed 24 months.

^c The EOT visit should occur within 7 days after the last dose of pexidartinib or at the time the decision is made to discontinue pexidartinib (if this is more than 7 days after the last dose of pexidartinib), unless there is a medical condition that prevents subjects from completing the visit within this time.

^d The End-of-Study will be reached with a follow-up phone call 1-month post-EOT visit to collect AE information.

^e BL2 MRI will need to be done within 14 days before treatment BL2 (window -14 days). Response should note “Progression” for those patients re-starting treatment. Assessments after re-treatment should use BL2 as the reference to determine Progression or Non-Progression.

^f Only subjects who end their study participation early with no radiologic disease progression will have an additional MRI at 3 months \pm 14 days after their last dose of study treatment or before any new TGCT therapy, including surgery, whichever occurs first. EOS will occur after this additional MRI.

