2. INTRODUCTION

2.1. Background

2.1.1. Tenosynovial Giant Cell Tumor (TGCT)

Tenosynovial giant cell tumor (TGCT) is a rare, nonmalignant neoplasm of the synovium, bursae, or tendon sheaths that is driven by overexpression of colony-stimulating factor-1 (CSF-1) often afflicting adults under 40 years of age. Annual TGCT incidence is estimated to be 43 cases per one million individuals, of which approximately 10% are of the diffuse subtype. Surgical resection, when feasible, is the standard treatment for TGCT; however, recurrence of the diffuse subtype is particularly common. Repeated surgeries often result in increasing morbidity and functional limitations of the affected joints. The diffuse disease often has more extensive involvement and a poorer likelihood of a successful cure with surgery, and therefore often may not be amenable to surgical resection due to the risk of morbidity or high risk of recurrence in diffuse disease. Systemic therapies targeting CSF-1 activity are being evaluated for the treatment of TGCT.

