6.2.2. Administration

Pexidartinib is provided as 200-mg capsules for oral, daily administration. Subjects are to be administered the dosage level at which they completed their prior study. Doses must be administered on an empty stomach (at least 1 hour before or 2 hours after a meal or snack), at approximately the same times of the day, and approximately 12 hours apart. Administration with food (particularly with high proportion of fat) may result in increased exposure to pexidartinib and should be avoided. Dose reductions and interruptions are permitted according to pre-specified guidelines.

On the day of the scheduled visit, subjects will be instructed to take their morning and evening dose at the usual time of study treatment. Subjects should be told to bring their bottle containing all unused study treatment to the clinic for accountability.

Between clinic visits, subjects will administer their study treatment at home and record the dosing information in the study dosing Diary. Missed doses (those generally outside of a \pm 2-hour dosing window) should be skipped and **NOT** administered as a double dose at the next dosing time point. Subjects who vomit their dose should be instructed **NOT** to make up that dose. Study sites will call subjects on a weekly basis as reminders to bring IP bottles to site visits and to complete their diaries. During these calls, study sites may also collect other information, including AEs and concomitant medications.

Further details on study treatment administration are contained in the *PLX3397-A-U4003 Pharmacy Manual*.

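### Table 1.1 schedules no pregnancy test between Baseline and End of Treatment, so during dosing in the Treatment Continuation Cohort the Section 8.4.2 stop rule rests on subject report or unscheduled testing

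*Combined protocol and SAP*

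**What the plan says.** Protocol Section 1.3, Table 1.1 covers the Treatment Continuation Cohort. Its serum pregnancy test row applies to a subgroup ("For females of reproductive potential (as defined in Section 5.1)") and is marked at Screening, Baseline and EOT. The cells for M3, M6, M9, M12, M15, M18 and M21 are empty. Footnote d on the Baseline cell reads "Urine pregnancy test at Screening only" and adds no later test.

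Three other statements fix the timing:

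- Section 1.2: "Screening and Baseline visits will occur on the same day".
- Table 1.1, footnote a: "The EOT visit should occur within 7 days after the last dose of pexidartinib", or when the decision to stop is made, if that is later.
- The same footnote: "The EOT visit must occur within 24 months after enrollment".

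Section 8.4.2 (Pregnancy Test) asks for a documented negative serum test, excludes anyone positive at Screening, and requires an enrolled subject who becomes pregnant on pexidartinib to stop the drug and tell the investigator. It gives no on-treatment test frequency. Neither the list of ongoing safety assessments in Section 4.1.1 nor Table 10.1 includes a pregnancy test.

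Table 1.3 covers the Re-Treatment period. It marks a serum pregnancy test at BL-2, M1/M2, M3, M6, M9, Mx and EOT.

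**The concern.** The protocol itself sets out the hazard. Section 8.4.2 reports malformations, post-implantation loss and abortion in rats and rabbits at roughly the human exposure at 800 mg, and Section 2.1.1 describes the disease as "often afflicting adults under 40 years of age". Continuation subjects take the drug daily for up to two years and receive a 3-month supply at each of the seven quarterly visits, with no scheduled pregnancy check at any of them.

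A rule that a pregnant subject must stop works only as fast as the pregnancy is noticed. If the plan is followed exactly, nothing scheduled between Baseline and EOT would reveal one. What is at stake is the length of fetal exposure before dosing stops, not the study's estimates.

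**Working it through.** No sample-size or power formula applies: the study has no hypothesis and its size is not statistically based (Sections 9.2 and 9.3). The check is a count of schedule cells plus interval arithmetic.

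**Inputs, all from Section 1.3, Table 1.1 and its notes**

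- A month is 30 days.
- EOT is at most 24 months after enrollment.
- Screening and Baseline are both day 0.
- Windows: ±7 days at M3, M6 and M9; ±14 days at M12, M15, M18 and M21.

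**Step 1. Longest interval under the plan.** 24 × 30 = 720 days from Baseline to the latest EOT. It is shorter for anyone who stops early.

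**Step 2. Scheduled tests that could prompt stopping on study.**

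| Test time | Role |
|---|---|
| Screening/Baseline (day 0) | A positive Screening result excludes the subject from enrollment |
| M3 to M21 (7 visits) | No test marked |
| EOT | Falls after the last dose in this study |

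Scheduled on-drug tests after Baseline: 0 of 7 visits.

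**Step 3. Are the blanks a loss in reading the table?** No. The row has its full 11 cells, and its last mark lines up with EOT. The liver function row, read the same way, is marked at Baseline, all seven quarterly visits and EOT.

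**Step 4. With a test at M3 to M21.** Scheduled on-drug tests become 7. The nominal gap is 90 days. The longest gap, with windows at opposite extremes, is:

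| Interval | Calculation | Days |
|---|---|---|
| Baseline to M3 | 90 + 7 | 97 |
| M3 to M6, M6 to M9 | 90 + 7 + 7 | 104 |
| M9 to M12 | 90 + 7 + 14 | 111 |
| M12 to M15, M15 to M18, M18 to M21 | 90 + 14 + 14 | 118 |
| M21 to latest EOT | 720 − (630 − 14) | 104 |

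The maximum is 118 days, against at most 720 now.

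**Step 5. Feasibility.** Hematology, chemistry, coagulation and liver tests are marked at all seven visits in Table 1.1, so blood is already being drawn. Table 1.3 already schedules the serum assay at M3, M6, M9 and Mx for re-treated subjects on the same drug.

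**The case against.** The strongest reply is that Section 8.4.2 does not make the stop rule depend on a scheduled test. The subject must stop and inform the investigator, so her report is enough. Section 7.1 lists pregnancy as a reason for discontinuation. Section 6.2.2 adds regular contact: "Study sites will call subjects on a weekly basis", and adverse events may be collected on those calls. Continuation subjects are established users who enter with a negative urine test confirmed by serum and with advice to use non-hormonal contraception. No section promises on-treatment testing in this cohort, so no stated requirement is breached.

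Much of this stands. A reader might infer that the rule cannot operate in this cohort. The documents do not support that, because self-report or an unscheduled test can trigger it. What remains is that none of these safeguards is a scheduled test.

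Three further inferences also go too far:

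- **That Tables 1.1 and 1.3 contradict each other.** Re-treated subjects come off a treatment-free period, and for them "A drug supply for more than 3 months may be dispensed". The two groups may reasonably be handled differently. Table 1.3 shows only that quarterly serum testing is workable in this study.
- **That the EOT test is of no protective use.** It cannot shorten dosing already given on study. Section 4.1.4, however, provides for post-trial access for subjects who are benefiting, and a positive EOT result would matter before that.
- **That the number of affected pregnancies can be stated.** The documents give neither the number of women of reproductive potential nor a pregnancy rate, and testing would not change how many pregnancies occur.

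**Conclusion.** The point holds as a subject-safety gap of limited weight. In the Treatment Continuation Cohort no pregnancy test is scheduled at any of the seven visits between Baseline and EOT, an interval of at most 720 days. During on-study dosing, detection is therefore left to the subject or to an unscheduled test, for a drug the protocol says may harm a fetus. The counts 0, 7, 720, 90 and 118 follow from Table 1.1 alone; the last two describe the schedule with quarterly testing added.

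How much undetected exposure quarterly testing would save cannot be calculated from the documents, because that depends on how soon subjects would notice a pregnancy themselves. With tests 90 days apart it would shorten undetected exposure without preventing all early exposure. A reader might also look for an effect on the results. There is none: no endpoint, estimate or planned comparison depends on this row. I would class it as a cheap improvement.

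**What to change.** In Table 1.1, mark the serum pregnancy test row at M3, M6, M9, M12, M15, M18 and M21 for females of reproductive potential, run on the blood already drawn at those visits. In Section 8.4.2 (Pregnancy Test), state that testing on treatment is quarterly. Do not hold dispensing for the result, so that daily dosing is not interrupted. Because the added test is serum, footnote d can stay as it is.

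The cost is up to seven inexpensive assays per subject in this subgroup, with no added visit. The change also needs an amendment with the IRB, IEC or authority approvals required by Section 10.1.1, across sites in the US, four EU countries, Australia and Taiwan. If the subject information is revised, it needs ethics re-approval and renewed consent. It would be sensible to carry the change in the next amendment made for other reasons, if one is near.
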